6.2.2 Dose Adjustment Guidelines for Selinexor Related Toxicities

All selinexor related non-hematological toxicities except those mentioned in the table below should be handled as follows:

Interrupt selinexor dosing in case of grade ≥ 3 non-hematological toxicity and resume dosing when resolved to grade 1 or less. Reduce selinexor dose by one dose level.

Table 3. Suggested Supportive Care and Dose Adjustment Guidelines for AEs Related to Selinexor (according to IB v 9)

Adverse Event	Occurrence	Action
Hematologic Adverse Events		
Thrombocytopenia		
Platelet count $25 \times 10^9/L$ to $<75 \times 10^9/L$	Any	
 Reduce selinexor by 1 dose level (see Table 2) Consider additional supportive care and discuss with Sponsor-Investigator
Platelet count $25 \times 10^9/L$ to $<75 \times 10^9/L$ with concurrent bleeding	Any	
 Interrupt selinexor Restart selinexor at 1 dose level lower after bleeding has resolved (see Table 2) Consider additional supportive care and discuss with Sponsor-Investigator
Platelet count $<25 \times 10^9/L$	Any	
 Interrupt selinexor Monitor until platelet count returns to at least $50 \times 10^9/L$ Restart selinexor at 1 dose level lower (see Table 2) Consider additional supportive care and discuss with Sponsor-Investigator
Neutropenia		

ANC 0.5 to $1.0 \times 10^9/L$ without fever	Any	
 Initiate growth factor support
ANC $<0.5 \times 10^9/L$ OR febrile neutropenia	Any	
 Interrupt selinexor Monitor until ANC returns to $\geq 1.0 \times 10^9/L$ Restart selinexor at 1 dose level lower (see Table 2) Initiate growth factor support
Anemia		
Hb $<8.0 \text{ g/dL}$	Any	
 Administer blood transfusions and/or other treatments per clinical guidelines

Adverse Event	Occurrence	Action
Life-threatening consequences (urgent intervention indicated)	Any	
 Interrupt selinexor Monitor until Hb returns to $\geq 8.0 \text{ g/dL}$ Restart selinexor at 1 dose level lower (see Table 2) Administer blood transfusions and/or other treatments per clinical guidelines
Nonhematologic Adverse Events		
Hyponatremia		

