Sodium $\leq 130 \text{ mmol/L}$	First	
 Interrupt selinexor and provide appropriate supportive care Monitor until sodium returns to $>130 \text{ mmol/L}$ Restart selinexor at same dose
	Second	
 Interrupt selinexor and provide appropriate supportive care Monitor until sodium returns to $>130 \text{ mmol/L}$ Restart selinexor at 1 dose lower (see Table 2)
Fatigue		
Grade 2 lasting >7 days OR Grade 3	Any	
 Interrupt selinexor and provide appropriate supportive care Add methylphenidate Monitor until fatigue resolves to Grade 1 or baseline Restart selinexor at 1 dose level lower (see Table 2)
Nausea and Vomiting		

Grade 1 or 2 nausea OR Grade 1 or 2 vomiting	Any	
 Maintain selinexor and initiate additional anti-nausea medications
Grade 3 nausea OR Grade ≥ 3 vomiting	Any	
 Interrupt selinexor Monitor until nausea or vomiting has resolved to \leqGrade 2 or baseline. Initiate additional anti-nausea medications Restart selinexor at 1 dose level lower (see Table 2)
Adverse Event	Occurrence	Action
Diarrhea		
Grade 2	First	
 Maintain selinexor and institute supportive care
	Second and subsequent	
 Reduce selinexor by 1 dose level (see Table 2) Institute supportive care
Grade ≥ 3	Any	
 Interrupt selinexor and institute supportive care Monitor until diarrhea resolves to Grade ≤ 2 Restart selinexor at 1 dose level lower (see Table 2)
Weight Loss and Anorexia		
Weight loss of 10% to $<20\%$ OR anorexia associated with significant weight loss or malnutrition	Any	
 Interrupt selinexor and institute supportive care Monitor until weight returns to $>90\%$ of baseline weight Restart selinexor at 1 dose level lower (see Table 2)
Other Nonhematologic Adverse Events		
Grade 3 or 4	Any	
 Interrupt selinexor and institute supportive care Monitor until resolved to \leqGrade 2 Restart selinexor at 1 dose level lower (see Table 2)

Conditions Not Requiring Selinexor Dose Reduction

The following conditions are exceptions to the dose-modification guidelines. Selinexor does not need to be held for alopecia of any grade, or forelectrolyte or serum analyte (e.g., urate) abnormalities that are reversible with standard interventions

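### Table 3's weight-loss and anorexia row applies one weight-only restart test to two different triggers, and no line names a weight loss of 20% or more

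*Combined protocol and SAP*

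**What the plan says.** All the relevant text is in section 6.2.2 and its Table 3.

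- **First trigger of the Weight Loss and Anorexia row.** It opens "Weight loss of 10% to" and closes at below 20%.
- **Second trigger, joined to the first by OR.** "anorexia associated with significant weight loss or malnutrition". Neither significant weight loss nor malnutrition is given a figure, and the below-20% limit is not attached to this trigger.
- **Action, the same for both triggers.** Interrupt, give supportive care, then "Monitor until weight returns to" above 90% of baseline, and restart one dose level lower.
- **Lead rule, in the text before the table.** Its scope is "All selinexor related non-hematological toxicities except those mentioned in the table below should be handled as follows". Its content is "Interrupt selinexor dosing in case of grade ≥ 3 non-hematological toxicity and resume dosing when resolved to grade 1 or less", with a reduction of one dose level.
- **Catch-all row at the end of the table.** Under "Other Nonhematologic Adverse Events" it covers grade 3 or 4 events, with the instruction "Monitor until resolved to" grade 2 or less, and restart one dose level lower.

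The Dose Reduction Guidelines in section 6.2.1 say that Table 3 is applied by CTCAE v4.03 grade. This row is written in percentages, and the documents do not say which grade corresponds to which percentage of weight loss.

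**The concern.** A restart test should ask whether the problem that caused the hold has resolved. Elsewhere Table 3 does this: in the platelet row with bleeding, the bleeding must stop; sodium must rise above 130 mmol/L; fatigue must fall to grade 1 or baseline. Here one of the two reasons for holding the drug concerns appetite and nutrition, yet the only recovery condition is a body weight that the patient may never have dropped below.

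The upper end of the row raises a second question. Several other rows run to the severe end (platelets below 25, neutrophils below 0.5, diarrhea of grade 3 or more). The numeric weight band stops at 20%, and the text does not say where a larger loss goes.

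The row is likely to be used. Section 1.1.4.2 reports anorexia in 51.0% of patients in company-sponsored trials, although it calls the listed events generally low-grade and reversible. Section 1.1.5 reports dose reduction or discontinuation for toxicity in 10 of the first 16 patients, with loss of appetite among the typical causes of reduction, before the starting dose was lowered. At stake are patient safety and uniform conduct: sites whose data are pooled (section 8.1) could hold and restart differently on the same findings, which would blur the dose intensity behind the response and tolerability results. The documents do not allow that effect to be sized.

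**Working it through.** The plan gives no calculated figure to reproduce. The check is threshold arithmetic on the row, followed by a comparison of the rules.

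**Step 1. Inputs (Table 3, Weight Loss and Anorexia row).**
- Weight as % of baseline = 100 − loss %.
- The first trigger fires if 10 ≤ loss < 20.
- The restart test is met if weight > 90, that is, if loss < 10.

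**Step 2. Is the restart test already met when the hold starts?**

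| Loss, % | Weight, % of baseline | First trigger fires | Restart test already met |
|---|---|---|---|
| 0 | 100 | no | yes |
| 5 | 95 | no | yes |
| 8 | 92 | no | yes |
| 9.9 | 90.1 | no | yes |
| 10 | 90 | yes | no |
| 15 | 85 | yes | no |
| 19.9 | 80.1 | yes | no |
| 20 | 80 | no | no |
| 25 | 75 | no | no |

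Wherever the first trigger fires, the restart test is not yet met, so the two fit together. At any loss below 10%, a patient can be held only under the second trigger, and the restart test is then met from the outset. This needs no assumption about grades. It needs only a patient with anorexia and malnutrition who has lost less than 10%, which the wording permits because malnutrition stands as an alternative to significant weight loss.

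**Step 3. Where does a loss of 20% or more go?** The first trigger no longer fires. What remains depends on whether anorexia is present.
- *With anorexia, and the loss judged significant:* the second trigger has no upper limit, so the patient can stay in the row with the 90% test.
- *Without anorexia:* three readings are open.
  1. The lead rule applies, and dosing resumes at grade 1 or less. But it excludes toxicities mentioned in the table, and weight loss is mentioned there.
  2. The catch-all row applies, and dosing restarts at grade 2 or less. But it is for other events, and weight loss has its own row.
  3. Neither applies, because weight loss is a named event, and the text gives no instruction.

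Readings 1 and 2 also need the event to be grade 3 or higher. The documents do not say whether a 20% loss is.

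**Step 4. Do the two general rules agree?** Each claims the nonhematologic events that have no row of their own. For a grade 3 event that has improved to grade 2, the catch-all row permits restart and the lead rule does not. They contradict each other, here and for any other event left to them.

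**The case against.** The strongest reply is that the row is workable in practice. Table 3 is headed as suggestions. Even when the weight test is met at once, the row still orders interruption, supportive care and a lower dose level on restart. The word returns suggests that the test was written for patients already below 90%. Section 6.2.1 adds intake logs, dietary counselling and continued nutritional assessment, and section 3.1.2 leaves stopping treatment to the investigator. All of this stands and limits the severity. None of it supplies a recovery condition for the second trigger.

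Three stronger readings are tempting, and the documents do not support them.

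- *The second trigger produces no hold at all.* It does produce one, and a dose reduction follows. What is missing is a condition that says when the hold should end.
- *Every loss of 20% or more leaves the row for the general rules.* The upper limit binds only the first trigger, so a patient with anorexia may remain in the row.
- *The worse weight loss gets the looser restart condition.* This needs a patient without anorexia, the catch-all row as the governing rule, and CTCAE grade limits that the documents do not give. Even if one assumes that 10% to below 20% is grade 2 and that 20% or more is grade 3, the answer depends on the rule chosen. The catch-all row would then allow restart inside the band that orders interruption. The lead rule would require a loss below 10%, about the same as the row's own test.

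One could also read the catch-all row as bringing every event into the table. That removes the conflict in step 4 only by leaving the lead rule nothing to govern.

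**Conclusion.** The point holds on two counts. First, the restart test does not match the second trigger: for anorexia with malnutrition at a loss below 10%, it is met when the hold starts, and improvement in the condition that prompted the hold is never asked for. This follows from the row alone. Second, the row does not name a loss of 20% or more. Such a patient may stay in the row if anorexia is present. Otherwise the governing rule is unclear, and the two candidate rules contradict each other.

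The size is minor to moderate. Every route through a stated rule restarts one dose level lower, so the defect concerns when dosing resumes and which rule covers the patient, not the dose level on restart. The documents do not show how many patients would be affected: the 51.0% is anorexia of any severity in other trials, not malnutrition or a loss of 20% or more. No difference in kilograms, and no reversed ordering of severity, can be claimed without grade limits from outside the documents.

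**What to change.** In the next amendment the sponsor should:

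- reconcile the row's two triggers with its restart condition, so that each trigger has a condition that addresses it;
- reconcile the row's upper limit with the lead rule of 6.2.2 and with the catch-all row, and state which rule governs a loss of 20% or more, with and without anorexia;
- reconcile the recovery grades of the lead rule and the catch-all row with each other.

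The clinical values are for the sponsor to set.

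The cost is a table edit and a note to sites in both trials. Weight is already scheduled at on-treatment visits in the flow chart. If the sponsor chooses a restart condition that uses more than weight, a small addition to the schedule may be needed: nutritional consultation is scheduled only at screening, and albumin is not in the limited chemistry used from cycle 3.

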1.1.5 Dosing rationale

An analysis of Phase 1 patient data showed that patients receiving doses ≤60 mg stayed on study longer than patients receiving doses ≥65 mg (120 days vs 90 days). In addition, a higher percentage of patients receiving 60 mg stayed on study ≥4 months as compared to patients receiving doses ≥65 mg (27% vs 19%). The 60 mg dose was associated with maximal responses (CR, PR, SD). These data supported 60 mg as the RP2D when the current study originally was designed. However, tolerability seems poorer than expected among the first 16 patients included in total in the EU and US studies. Either dose reductions or discontinuation of treatment due to toxicity have been necessary in ten out of 16 patients and

consequently most patients have been treated at 40 mg twice weekly for three weeks in a four week schedule. In general, toxicities resulting in dose reductions were typically nausea, vomiting, loss of appetite and fatigue followed by grade 4 thrombocytopenia (n=1) and severe pneumonia. Based on these data, the starting dose going forward will be 40 mg twice weekly.

Recent analysis of the existing PK data from Phase 1 trials KCP-330-001 and KCP-330-002 supports the use of fixed rather than BSA-based dosing. The 5th and 95th percentile for BSA values encountered to date in Phase 1 trials KCP-330-001 and KCP-330-002 are 1.5 and 2.3 m², respectively (N=331). PK values (C_{max} and AUC(0-∞)) for a given flat (fixed) dose of selinexor were similar across this typical BSA range, indicating that exposure is not strongly correlated with BSA.

Currently the dosing schedule for selinexor in phase II trials is twice weekly (Day 1 and 3) during each week. This schedule is supported by pharmacodynamics studies showing selinexor binding to its XPO1 target persisted for at least 48 hours. A dosing regimen of 10 doses per Cycle (3 doses during weeks 1 and 3, 2 doses during weeks 2 and 4) was evaluated in Phase 1 studies and found to be less tolerated than the twice weekly (8 doses per Cycle) regimen, supporting the use of the twice weekly dosing regimen as the preferred regimen (Chen C et al, ASH 2015).

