Selinexor-induced anemia may contribute to dizziness, confusion, syncope and/or fatigue, particularly in elderly patients and patients who are at greater risk of cognitive sequelae. Per NCCN Guidelines, treatment with RBC transfusions and/or growth factors, per institutional guidelines, should be considered for patients with symptomatic anemia.

Other Adverse Events Observed during Studies

Vision Blurred and Cataracts

Patients reporting blurry vision or other visual changes should be evaluated by an ophthalmologist. Nearly all cases of treatment emergent visual changes have not been associated with objective findings. Changes in lens prescriptions and/or wetting drops may improve vision. Blurred vision associated with selinexor use is typically self-limited, and dosing can usually be maintained at the same level and frequency.

Patients who are at risk of cataract formation, or have cataracts present at baseline, should be monitored for changes in lens opacity. If changes in lens opacity are observed, the patient should be evaluated by an ophthalmologist. In selinexor clinical studies, several patients have undergone cataract surgery with minimal to no interruption of selinexor dosing and without complications.

Hyponatremia

Investigators should rule out the possibility of pseudo-hyponatremia due to elevated glucose (or monoclonal protein) levels. Abnormal serum sodium levels should be corrected. Adequate fluid and caloric intake, including electrolyte-rich beverages instead of plain water, has led to reversal of hyponatremia. Diuretic use should be addressed and possibly stopped, and salt supplements should be considered. If hyponatremia persists, cardiac, hepatic, adrenal, renal and thyroid disorders, along with the Syndrome of Inappropriate Antidiuretic Hormone Secretion (SIADH), and Fanconi syndrome should be ruled out.

Infection

Appropriate broad-spectrum intravenous antibiotics and antifungal agents should be started immediately in patients who develop fever or other signs of systemic infection. Selinexor should be suspended in any patient with Grade 4 infection or sepsis (even in the absence of documented infection) until the patient's clinical condition is stabilized. Selinexor can then be re-started at the same dose once the patient's clinical status has stabilized, even in the setting of continued intravenous antibacterial or other anti-microbial

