Selinexor Dose Adjustment in the Setting of Infection

In patients who develop fever or other signs of systemic infection, appropriate antimicrobial should be initiated immediately. Selinexor should be withheld in any patient with active uncontrolled infection, any Grade 4 infection or sepsis (even in the absence of documented infection) until the patient is clinically stable. After the infection has stabilized clinically or resolved, Selinexor treatment may continue at the original dose. Missed doses will not be replaced. Patients may continue on antibiotics for prolonged periods while re-initiating their Selinexor regimen at the discretion of the investigator. Selinexor is not known to have any drug interactions with standard antimicrobials.

Prophylactic antibiotics are permitted concurrently with Selinexor treatment, but are not recommended for most patients. Patients with a history of recurrent infections or those at high risk for specific infections may continue their prophylactic antimicrobial regimens without modification when initiating selinexor therapy. In a randomised study in old patients with acute myeloid leukemia (AML), sepsis occurred more frequently in patients receiving Selinexor compared with patients receiving physician's choice of therapy.

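### For a severe infection judged related to selinexor, the dose-adjustment rules and the infection text give different restart doses, and the protocol does not say which governs

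*Combined protocol and SAP*

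**What the plan says.** Two sets of instructions bear on the dose after a severe infection.

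**Infection text.** The infection subsection of 6.2.2 sets its triggers: "Selinexor should be withheld in any patient with active uncontrolled infection, any Grade 4 infection or sepsis". It then says: "After the infection has stabilized clinically or resolved, Selinexor treatment may continue at the original dose". The infection paragraph of 6.2.1 names Grade 4 infection and sepsis only, and says "Selinexor can then be re-started at the same dose once the" patient has stabilised. Neither is limited to events caused by selinexor.

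**Dose-reduction rules.** The lead rule of 6.2.2 opens: "All selinexor related non-hematological toxicities except those mentioned in the table below should be handled as follows". For Grade 3 or higher it calls for interruption, and then: "Reduce selinexor dose by one dose level". Table 3, which covers events related to selinexor, has no infection row. It does have a row headed "Other Nonhematologic Adverse Events", under which a Grade 3 or 4 event restarts one level lower. Its severe neutropenia row, which includes the words "OR febrile neutropenia", also restarts one level lower.

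**Exceptions and tie-break.** The exceptions after Table 3 are alopecia and reversible electrolyte or analyte abnormalities. Section 6.2.1 adds that when several types of toxicity coincide, the worst grade decides the modification.

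**The concern.** A Grade 4 infection that the investigator attributes to selinexor falls under both sets of instructions. One set takes the patient down a level; the other allows the previous dose. Two investigators who each follow the written text could therefore restart the same patient at different doses.

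The events in question are the most serious infections. The infection subsection itself reports that sepsis was more frequent on selinexor in a randomised study of older patients with AML. That is a different population, but it makes a judgement of relatedness foreseeable. Safety and tolerability are a secondary objective, and US and EU data are to be pooled (8.1), so uneven handling would also blur what the trial reports about dose reductions.

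**Working it through.** The protocol states no statistical figure on this point. The check is a comparison of texts, followed by dose arithmetic from Table 2.

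**Step 1: which texts reach which event**

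| Event | Lead rule or Table 3 'Other' row (6.2.2) | Infection text (6.2.1, 6.2.2) | Conflict? |
|---|---|---|---|
| Unrelated infection, any grade | Does not apply (related events only) | Same or original dose allowed, if triggered | No |
| Related Grade 3, controlled, not septic | One level lower | Withholding not triggered | No |
| Related Grade 3, septic | One level lower | Same or original dose allowed (both sections) | Yes |
| Related Grade 3, uncontrolled, not septic | One level lower | Original dose allowed (6.2.2 only) | Yes |
| Related Grade 4 | One level lower | Same or original dose allowed (both sections) | Yes |

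The lead rule excludes toxicities that Table 3 mentions. Whether infection counts as mentioned through the 'Other' row makes no difference to the dose, because both routes lead one level lower. They do differ on when to resume: Grade 1 or less under the lead rule, Grade 2 or less under the 'Other' row.

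**Step 2: does any text settle it?** The exceptions list omits infection. Neither infection text says that it overrides the lead rule or Table 3. The infection paragraph of 6.2.1 refers the reader to a section 6.1.3, which the protocol does not contain. The tie-break selects among different toxicities; it cannot choose between two rules for one infection.

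**Step 3: related febrile neutropenia with sepsis.** Here two specific entries apply: the neutropenia row (one level lower) and the infection text (original dose allowed). If the neutropenia has the higher grade, the tie-break points to its row. If the sepsis has the higher grade, the question from Step 1 returns. If the grades are equal, the tie-break is silent.

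**Step 4: size.** Each 28-day cycle has three dosing weeks, so dose per cycle = weekly dose × 3.

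- Level 0: (40 + 40) × 3 = 240 mg
- Level -1: (20 + 40) × 3 = 180 mg
- Level -2: 40 × 3 = 120 mg
- Level -3: 20 × 3 = 60 mg
- Level -4: discontinue

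| Level when interrupted | Same dose | One level lower | Difference |
|---|---|---|---|
| 0 | 240 mg | 180 mg | 60/240 = 25% |
| -1 | 180 mg | 120 mg | 60/180 = 33% |
| -2 | 120 mg | 60 mg | 60/120 = 50% |
| -3 | 60 mg | discontinue | continue versus stop |

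**The case against.** The best defence is that the specific rule overrides the general one. The infection text in 6.2.2 is a dedicated subsection placed after the general table, and 6.2.1 agrees with it. The wording is also permissive (may, can), while Table 3 is titled as suggestions. An investigator who always restarts one level lower therefore breaches nothing in the infection text.

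Part of this stands. The two sets are not flat opposites, and reading the infection text as the governing one is natural. But the protocol never says so, and febrile neutropenia with sepsis meets two specific entries, so the principle does not settle that case. The permissive wording does not help the investigator who restarts at the same dose: that follows the infection text and departs from the lead rule, which is not labelled as a suggestion.

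Three stronger readings are tempting and not supported:

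- **That every severe infection is affected.** The lead rule and Table 3 cover related events only, and section 7.6 requires that study treatment be the more likely explanation. Controlled, non-septic Grade 3 infections do not trigger the withholding rule.
- **That the protocol has no precedence rule at all.** It has the tie-break for concurrent toxicities, which can decide some cases of febrile neutropenia with sepsis.
- **That sites are already departing from the infection text.** Section 1.1.5 lists "grade 4 thrombocytopenia (n=1) and severe pneumonia" among toxicities that led to dose reductions. Those were the first 16 patients across the EU and US studies, from the period when 60 mg was the planned dose; the infection rule then in force is not shown, and a reduction is compatible with permissive wording.

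**Conclusion.** The concern holds within stated limits. For an infection judged related to selinexor that is Grade 4, or Grade 3 and septic or uncontrolled, the protocol directs a restart one level lower in one place and allows the same or original dose in another, without saying which governs. Related febrile neutropenia with sepsis meets a similar overlap that the tie-break resolves only in part.

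The gap is one dose level: 25% to 50% of the dose per cycle, or continuing versus discontinuing at level -3. This assumes that the original dose means the dose at interruption, as 6.2.1 suggests. The number of patients affected cannot be estimated, because the documents give no frequency of related severe infection.

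The consequence is for consistent dosing, patient safety and the reporting of tolerability. A reader might infer an effect on the response-rate test, but nothing in the sample size or error rates depends on these rules.

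**What to change.** The sponsor should reconcile the infection paragraph and the concurrent-toxicity tie-break in 6.2.1 with the lead rule, the Table 3 neutropenia and 'Other' rows, the exceptions list and the infection subsection in 6.2.2. One precedence sentence or one infection row in Table 3 would be enough. It should say which text governs a related severe infection, and which governs when febrile neutropenia and sepsis occur together. The same edit can align the two resumption grades (Step 1) and correct the reference to section 6.1.3.

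Which dose applies is a clinical decision for the sponsor, and this review takes no view on it. The cost is a short protocol amendment with the usual approvals; no design or analysis change is needed.
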